4. STUDY ENDPOINTS

4.1. Primary Efficacy Endpoint

- Proportion of Responders (≥ 20, 30, 40, 60 and 70% reduction in the means of the ADPSs from the BPI-DPN) from the 7 days prior to the Day 0 Visit to the 7 days prior to the Day 90 Visit and the 7 days prior to the Day 180 Visit for Engensis compared to Placebo
- Changes in the means of the Average Daily Pain Scores (ADPSs) from the BPI-DPN from the 7 days prior to the Day 0 Visit to the 7 days prior to the Day 90 Visit for Engensis compared to Placebo
 - This will be calculated the same way described in Section 4.1.
- Changes in the severity scores (Average Pain, Worst Pain, Least Pain and Pain Right Now)
 from the full BPI-DPN from the 7 days prior to the Day 0 Visit to the 7 days prior to the Day
 90 Visit and to the 7 days prior to the Day 180 Visit for Engensis compared to Placebo
 - The severity score consists of four scores (Average Pain, Worst Pain, Least Pain and Pain Right Now), and the overall average of the scores can be calculated. The change in each score will be calculated and analyzed separately.
- Changes in Michigan Neuropathy Screening Instrument (MNSI) from Baseline to Day 90 and to Day 180 for Engensis compared to Placebo
 - The MNSI comprises a Participant questionnaire (15 questions) with two domains: Physical Assessment and History. The change will be calculated for each domain separately.
- Changes in Quality of Life in the 36-item Short Form Health Survey (SF-36) from Baseline to Day 90 and to Day 180 for Engensis compared to Placebo
 - The SF-36 survey has 8 domains and 2 component scores; the 8 domains include Physical Functioning, Social Functioning, Role—Physical, Role—Emotional, Bodily Pain, General Health, Vitality, and Mental Health, and the 2 component scores include a Physical Component score and Mental Component score. The change will be calculated for each domain and component score separately.
- Changes in Quality of Life in the EuroQol Health Utilities Index (EQ-5D) from Baseline to Day 90 and Day 180 for Engensis compared to Placebo
 - EQ-5D has 2 main parts. Part 1 is the descriptive system and Part 2 is the visual analog scale of self-rated health. Part 1 consists of 5 questions assessing: Mobility, Self-Care, Usual Activities, Anxiety/Depression and Pain/Discomfort. The overall health state value index combining the 5 questions of Part 1 in EQ-5D will be calculated. The overall scores and change in each Part will be calculated and summarized.

4.4. Safety Outcomes

Safety analyses in this study will evaluate the safety profile of Engensis as compared with Placebo. No formal statistical testing will be conducted for the safety analyses. All participants in the safety subset will be included in these analyses. Participants will be grouped by treatment received. All summaries will be derived based on available data. No imputation will be performed for missing values. All safety analyses will be made on the Safety Population.

- Change from Baseline (Day 0) in the cytokine profile through post-dose to Day 104 for Engensis compared to Placebo
- Presence of anti-hepatocyte growth factor (HGF) antibodies following Engensis administration compared to Placebo
 - HGF antibodies will be collected on Day 0, 60, 90, 150 and 180, and the presence will be summarized according to each time point.
- Adverse events
- · Injection site reaction assessment
- Vital signs
 - Blood pressure
 - Weight
 - Heart rate
 - Respiration rate
 - Oxygen saturation
 - Temperature
- HbA1c
- Laboratory values (Serum chemistry and hematology)
- Retinal fundoscopy

4.5. Other Clinical Parameters

Total acetaminophen (rescue medication) used during the study

4.6. Planned Covariates

As defined in the analysis of the primary and secondary efficacy endpoints, the following can be included in the model as covariates after testing their significance:

- Baseline pain score
- Baseline HbA1c (< and \ge median)
- Gender (male and female)
- Age (<65 years and ≥ 65 years)

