### **6.3.2. Stratification**

Participants will be stratified between the Engensis and Placebo groups according to their baseline ADPSs of  $< 7$  and  $\geq 7$ . The ADPS for the baseline determination will be considered missing if fewer than 5 of 7 days of the ADPS entries are provided. Participants will not be

randomized if the baseline ADPS has fewer than 5 days of the ADPS entries.

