6.5. Subgroup Analysis Subsets

The subgroup analyses will be exploratory in nature and will be conducted in the ITT population. The primary and secondary efficacy endpoints will be evaluated based on the categories of the covariates described in Section 4.6 as well as the stratification factor. These subgroups that will be re-examined and may be recategorized or eliminated due to small sample size (if there are <10% of participants within each subgroup) before unblinding for analysis. For example, if <10% of overall participants are \geq 65 years, then analyses for this subgroup will not be performed. The treatment by subgroup interaction will be examined and tested as described in Section 8.4.5.

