7.6.1. Missing Pain Scores for the Average Scores from BPI-DPN

The means of the Average Daily Pain Scores (Question 5 from the BPI-DPN) for a visit will be considered as missing if fewer than 5 of 7 days of BPI-DPN eDiary entries are provided. Any missing mean pain score of ADPS will be imputed using the methods described below.

- Multiple Imputation (MI) method:
 - Step 1: Intermittent missing values will first be imputed by treatment group using the Markov Chain Monte Carlo (MCMC) method, resulting in data with a monotone pattern.
 - Step 2: Multiple imputation by treatment group using linear mixed model regression with factors of baseline pain score, baseline HbA1c, gender, and age will be applied to the data

obtained from the MCMC step. The imputed score will be rounded to the first decimal point.

The entire procedure will be repeated 10 times, and 10 complete datasets will be used for the analysis.

Mean of the other group (MOTH):⁴

- 1. For a participant with missing average pain score/the worst pain score in the full BPI-DPN instrument from the 7 days prior to the Day 0 to Day 90, and Day 180 visits, identify the participant's following baseline characteristics:
 - Study treatment group
 - o Baseline Average Daily Pain Score (<median or ≥median)
 - HbA1c (<median or ≥median)
 - o Gender (male or female)
 - Age (<65 years and ≥65 years)
- 2. The missing mean pain score from the 7 days prior to the Day 0, Day 90, and Day 180 visits will be imputed by using the mean pain score obtained at the same time point of those participants in the other treatment group who match the participant's baseline characteristics. For example, for the missing pain scores of the Engensis participants, the mean pain scores of the placebo participants within the same covariate groups will be used to impute the missing pain scores.
- 3. The baseline characteristics will be re-examined for appropriateness and may be re-categorized (due to small sample size) before unblinding the study.
- 4. The imputed score will be rounded to the first decimal point. The imputed scores will be included in the continuous Repeated Measures Model (Section 8.4.1) analysis.

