8.7. Interim Assessment

The interim assessment will be conducted by the IDMC; the details of the procedure are described in the IDMC Charter. Given that much of the programming to derive the estimates will come from this SAP, a summary of the process is outlined below.

After 76 subjects either discontinue or complete the study, representing 50% of the original sample size, the interim analysis will be performed. The interim analysis will be used to re-estimate the sample size based on the following decision rule; the trial may be halted for futility based on the interim analysis results.

- If the conditional power is in the unfavorable zone, <39.6%, the study will be halted; no additional participants will be enrolled.
- If the conditional power is in the promising zone, 39.6% to 80%, the sample size will be increased to a final sample size (N₂, ≤250), where N₂ satisfies the condition that the conditional power is 80%.
- If the conditional power is in the favorable zone, >80%, the study will continue with the original sample size of 152.

The interim assessment will follow the method described in the published paper by Mehta and Pocock,² which states that if "the sample size is only increased when the interim conditional power falls within a certain 'promising zone' then the conventional test will indeed protect the type-I error." The minimum of conditional power is not so small as to result in an inflated overall type-I error using a conventional final analysis. Therefore, implementing the interim analysis for the reestimation of sample size should protect inflation of the type I error rate.

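### As worded, SAP 4.6 lets significance tests choose the model covariates, including baseline pain; fix the set in advance unless SAP 8.4.1 already does

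*SAP*

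**What the plan says.** SAP 4.6 (Planned Covariates) lists baseline pain score, baseline HbA1c, gender and age, introduced by "defined in the analysis of the primary and secondary efficacy endpoints, the following can be included in the model as covariates after testing their significance". It gives no test, significance level, dataset or timing.

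Other parts of the SAP are tighter:

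- SAP 6.5 allows subgroup categories to change, but they "may be recategorized or eliminated due to small sample size (if there are <10% of participants within each subgroup) before unblinding for analysis". It builds the subgroups from "the categories of the covariates described in Section 4.6 as well as the stratification factor", so the stratum is treated as separate from the 4.6 list.
- SAP 7.6.1, on matching categories for the mean-of-the-other-group imputation, says: "The baseline characteristics will be re-examined for appropriateness and may be re-categorized (due to small sample size) before unblinding the study".
- SAP 7.6.1 also names the same four variables as factors in the multiple imputation regression, with no test attached. That rule covers imputation only.

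The stratum comes from Protocol 6.3.2: "Participants will be stratified between the Engensis and Placebo groups according to their baseline ADPSs", cut at 7. The same section says that a participant will not be "randomized if the baseline ADPS has fewer than 5 days of the ADPS entries", so every randomised participant should have a baseline ADPS.

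The main model belongs to SAP 8.4.1. Section 7.6.1 says: "The imputed scores will be included in the continuous Repeated Measures Model (Section 8.4.1) analysis". The copy available runs from the 8.4 heading directly to 8.5, so that text cannot be read. For the interim look, SAP 8.7 says "the details of the procedure are described in the IDMC Charter"; the Charter was not supplied either. Protocol section 9 leaves the detailed methods to the SAP.

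**The concern.** A confirmatory analysis should have one model that is known before the outcome data are examined. Under 4.6 as worded, the model depends on which covariates pass a test that the section does not define. A joint model, one-at-a-time tests, tests with or without the treatment arm, backward elimination, and a 5% or 10% level would all fit the wording, and they need not choose the same set. The 10 imputed datasets of 7.6.1 add a further gap: a test could select different covariates in different datasets, and 4.6 does not say how that would be settled.

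Baseline pain is the covariate most worth securing. It is the starting value of the outcome, it is required for randomisation, and the randomisation is stratified on it. The 4.6 wording gives it no firmer place than gender or age. What is at stake is certainty about the model and about baseline adjustment, more than the error rate.

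**Working it through.** **Inputs from the documents.** SAP section 5: difference 1 point, SD of change 2.18, 1:1 allocation, two-sided 5%, target N = 152, stated power 0.802 (Table 4, scenario 1).

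**Assumed, because the documents do not give it.** The correlation r between baseline pain and change.

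**Step 1. Reproduce the plan's figure.** Normal approximation: n per arm = 2 × 2.18² × (1.960 + 0.842)² / 1² = 74.6, so 75 per arm or 150 in total, against the stated 152. A two-sided t-test at N = 152 has noncentrality 1 / (2.18 × √(4/152)) = 2.828 on 150 df, which gives power 0.8022. The plan's 0.802 is reproduced.

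**Step 2. How often a 5% test drops baseline pain.** With arm and baseline in the model, the test of baseline has noncentrality λ = r√152 / √(1 − r²) on 149 df, with critical value 1.976. The simulation column covers the 5% versions of joint, one-at-a-time (with and without arm) and backward-elimination testing.

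| r | λ | Dropped, closed form | Dropped, simulation |
|---|---|---|---|
| 0.15 | 1.87 | 54% | 53% to 57% |
| 0.2 | 2.52 | 29% | 28% to 32% |
| 0.3 | 3.88 | 2.9% | 2.5% to 3.7% |
| 0.4 | 5.38 | 0.04% | at most 0.1% |

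At a 10% level the simulated figures are 40% to 44% (r = 0.15) and 19% to 22% (r = 0.2).

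**Step 3. What adjustment for baseline is worth.** The residual SD is 2.18 × √(1 − r²). Power at N = 152 (noncentral t):

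| r | Residual SD | Power |
|---|---|---|
| 0 | 2.180 | 80.2% |
| 0.2 | 2.136 | 81.8% |
| 0.3 | 2.080 | 83.8% |
| 0.4 | 1.998 | 86.6% |

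These compare adjustment with no adjustment. They are not gains over a pretest, which at r = 0.3 or more nearly always keeps baseline pain.

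**Step 4. Effect on error rate, verdict and power.** Simulation of 10,000 trials per cell, r = 0.15 to 0.4, with eight testing rules (the four types in step 2, each at 5% and 10%). HbA1c, gender and age are either (A) unrelated to change or (B) each correlated 0.15 with it. Further assumptions: baseline ADPS normal with mean 6.3 and SD 1.4, truncated to 4–10; 40% aged 65 or over; 50% male; blocks of 4 within stratum.

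- Type I error: 4.4% to 5.6% for the eight rules, 4.4% to 5.3% for fixed baseline plus stratum (Monte Carlo SE about 0.2 points). A separate simulation with 8,000 runs per case also gave 4.4% to 5.6% for pretests.
- The eight rules do not all agree on p < 0.05 in 0.9% to 1.3% of trials (A) or 2.5% to 2.9% (B).
- Power of the rules is within 0.5 points of fixed baseline plus stratum in A and 0.7 to 2.1 points higher in B, where they pick up the other covariates.
- Adding the stratum to continuous baseline costs 0.1 to 0.4 points and leaves type I error unchanged.
- Including all four covariates, against baseline alone, costs 0.8 to 1.1 points in A and gains 1.8 to 1.9 in B.

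All runs are single-visit ANCOVA with complete data. The planned analysis is a repeated measures model with imputation, and the responder endpoint was not simulated.

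**The case against.** The strongest objection is that 4.6 is a pointer to the efficacy analysis sections, which exist but cannot be read here. Text missing from the copy is not missing from the plan. There are signs that the unread part held model detail: AIC is in the abbreviation list, and a reference on repeated measures analysis is in the reference list, yet neither is used in the text that survives. Section 7.6.1 also shows that the SAP can name the four variables outright. This objection stands as a limit. The point concerns the wording of 4.6, and 8.4.1 may already fix the set. If it does, the testing clause contradicts it and should still go.

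A second objection is that the consequences are small, and this stands too. Baseline pain is often dropped only where adjustment is worth little: at r = 0.2, 81.8% − 80.2% = 1.6 points. A pretest can even have more power than baseline plus stratum. Including the stratum beside continuous baseline is a matter of reflecting the randomisation, with no type I benefit in these runs.

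Three stronger readings are tempting, and the documents support none of them:

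- **Type I error is inflated.** Pretests applied mechanically stay near 5%. Material inflation would need someone to choose the most favourable model after seeing treatment results. Nothing says that the testing is unblinded, and SAP 7.3 unmasks the project team only after database lock.
- **The primary model has no fixed covariates.** That cannot be said with 8.4.1 unread.
- **The interim decision is affected.** That depends on a Charter that was not supplied, so it is only something to confirm.

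**Conclusion.** The point holds as a defect of wording with an inexpensive remedy. As written, 4.6 makes every covariate conditional on an undefined test, and no readable passage fixes the covariates of the primary or secondary models.

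The gain from fixing the set is one model known in advance and certain adjustment for baseline. The error rate is not at issue, and no net power gain over a pretest is promised. If r is 0.2 or less, a 5% test would leave baseline pain out of roughly 30% or more of trials; at 0.3 the figure is about 3%. These figures rest on an assumed r and a single-visit, complete-data model. Confidence is moderate, because 8.4.1 could reduce the matter to an edit of one clause.

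**What to change.** Before any unblinded interim data are seen:

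1. Remove from SAP 4.6 the condition that covariates enter only after a significance test.
2. State that the models always include the continuous baseline value of the endpoint's own score and the randomisation stratum. That means baseline ADPS for the primary and responder endpoints, and baseline Worst Pain for the Worst Pain endpoint.
3. Assign HbA1c, age and gender in advance, either to the model or to a named sensitivity analysis.
4. Confirm that 8.4.1, 8.7 and the IDMC Charter use this same model, and align their wording. If 8.4.1 already fixes the set, only 4.6 needs editing.

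The cost is SAP wording. The baseline scores come from the pre-Day 0 diary and the stratum from randomisation, so no participants or data are added. There is a possible price in power: 0.1 to 0.4 points for the stratum, and 0.7 to 2.1 points against a pretest if HbA1c, age and gender prove prognostic but are left out. Placing those three in the model instead gains 1.8 to 1.9 points over baseline alone in that case, and loses 0.8 to 1.1 if they are not prognostic.

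### SAP 4.6 plans HbA1c and age as two-level covariates and does not list the randomisation stratum; continuous coding plus the stratum would be a small, nearly free improvement

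*SAP*

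**What the plan says.** SAP 4.6 (Planned Covariates) says of the primary and secondary efficacy analyses that "the following can be included in the model as covariates after testing their significance". Four items follow:

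- "Baseline pain score", with no cut given;
- HbA1c, an entry that begins "Baseline HbA1c (<" and takes the median as its cut;
- gender;
- age, as "Age (<65 years and ≥ 65 years".

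Both split variables exist as measured values. Protocol 1.3 (Schedule of Activities footnotes) collects age at Screening and HbA1c levels at Screening, Day 90 and Day 180. Protocol 5.1 applies a numerical HbA1c limit of 10.0%.

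Protocol 6.3.2 sets the stratification: "Participants will be stratified between the Engensis and Placebo groups according to their baseline ADPSs", with the cut at 7. This factor is not among the four items. SAP 6.5 treats it as separate, since its subgroups are defined by "the covariates described in Section 4.6 as well as the stratification factor".

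SAP 7.6.1 uses the same four variables for imputation. Step 2 of the multiple imputation names them without cuts. The MOTH method uses two-level groups as matching cells. Neither uses the randomisation stratum.

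SAP 4.6 defers to the efficacy analysis section, but the text of SAP 8.4.1 to 8.4.6 is not in this copy. That is a limit of the copy, not a fault of the plan.

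**The concern.** Two-level groups are natural for subgroup tables. As adjustment terms they are weaker than the values they come from, because everyone on one side of the cut is treated as alike. If HbA1c or age predicts the change in pain, part of the precision that adjustment could give is discarded, although the data are already in hand.

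The stratum raises a different question. When randomisation is balanced within strata of a prognostic factor, and no term for that factor is in the model, the true variability of the treatment difference is smaller than the model's standard error suggests. The test is then conservative. Baseline pain, from which the stratum is cut, is on the 4.6 list, but its entry depends on a significance test, so it could in principle be left out.

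**Working it through.** **1. The plan's own figure.** Inputs from SAP 5: difference 1, SD 2.18, 1:1 allocation, two-sided 5%, N = 152. For a two-sample t-test with 76 per group, the noncentrality is 1/(2.18 × √(2/76)) = 2.83 on 150 degrees of freedom. Power is 0.8022, which matches the 0.802 in Table 4. The other seven rows, and the 82.4% for a difference of 0.8 at N = 250, reproduce in the same way. No covariate enters, so the stated power counts on no gain from adjustment.

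**2. What a split keeps.** For a normal covariate with a linear effect, a split with upper fraction p keeps φ(q)²/[p(1−p)] of its explained variance, where φ is the normal density and q the cut.

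- Median split: 0.3989²/0.25 = 0.637, so 36% is lost.
- A 60/40 split, assumed for age at 65: 0.622, so 38% is lost.

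**3. Cost for an assumed joint R².** Using 0.63 for both covariates, the residual variance ratio is (1 − 0.63R²)/(1 − R²). The equivalent loss of participants is N × (1 − 1/ratio).

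| Assumed joint R² | Variance ratio | Lost of 152 | Lost of 250 |
|---|---|---|---|
| 0.02 | 1.008 | 1 | 2 |
| 0.05 | 1.019 | 3 | 5 |
| 0.10 | 1.041 | 6 | 10 |

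**4. The same in power terms.** Assume that baseline pain is in the model with correlation 0.2, that HbA1c and age each have correlation r with the change, and that the covariates are independent; N = 152.

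| r | Power, continuous | Power, split | Lost of 152 |
|---|---|---|---|
| 0.05 | 0.820 | 0.819 | 0.3 |
| 0.1 | 0.826 | 0.823 | 1.2 |
| 0.2 | 0.850 | 0.838 | 5.0 |
| 0.3 | 0.889 | 0.863 | 12.0 |

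For example, at r = 0.2 the continuous model explains 0.04 + 2 × 0.04 = 0.12 and the split model 0.04 + 0.04 × (0.637 + 0.622) = 0.0904. The ratio is 0.9096/0.88 = 1.034. The last row is a joint R² of 0.18, beyond the range in step 3.

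**5. The stratum with and without baseline pain.** Simulation of 4,000 trials of 152, randomised 1:1 within the stratum, with baseline ADPS assumed normal (mean 6.5, SD 1.4) and restricted to 4–10. The table gives the mean standard error of the treatment difference.

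| Correlation of baseline pain with change | Neither | Stratum only | Continuous baseline | Both |
|---|---|---|---|---|
| 0.2 | 0.3532 | 0.3485 | 0.3463 | 0.3472 |
| 0.4 | 0.3535 | 0.3345 | 0.3240 | 0.3248 |

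With continuous baseline pain present, adding the stratum gains nothing under a linear relation. With neither term, the standard error is 0.3532/0.3485 = 1.01 to 0.3535/0.3345 = 1.06 times that of the stratum-only model.

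**6. Actual alpha if both are absent.** Assume 30% of participants at ADPS 7 or above; the stratum then carries 0.576 of the baseline R². The effective critical value is 1.96/√(1 − 0.576r²).

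- r = 0.2: 1.96/√0.977 = 1.98, alpha about 4.7%.
- r = 0.3: 1.96/√0.948 = 2.01, alpha about 4.4%.

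**7. How likely baseline pain is to be dropped.** The SAP gives no level for the significance test. At an assumed 5% and n = 152, baseline pain would fail about 30% of the time at r = 0.2 and about 3.5% at r = 0.3.

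**The case against.** The strongest reply is that the model itself cannot be read. SAP 4.6 defers to sections whose text is absent here, and SAP 6.5 shows only that the stratum is outside the 4.6 list. A reader might infer that the efficacy models omit the stratum and so waste precision. The documents do not support this: omission from the model cannot be confirmed, and the stratum is a coarse cut of a variable that 4.6 already lists uncut. This part of the reply stands.

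A reader might also infer a marked fall in type I error. At a correlation of 0.5 the formula in step 6 gives about 3.4%. But that requires baseline pain to fail its test, and at n = 152 a correlation that strong would pass a 5% test almost every time. The plausible range is the 4.7% to 4.4% shown, and the error is in the conservative direction.

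Third, a reader might infer harm at the interim, because a sample-median cut can move between the interim and final data. SAP 8.7 and 8.7.1 do not say that conditional power comes from a covariate-adjusted model, and the details lie in the IDMC Charter, so no effect is shown.

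Finally, the listed covariates only may enter, the size of any loss is assumed, and weak covariates lose almost nothing. All of this is correct and limits the weight of the point. It does not remove the reason to prefer measured values. MOTH does need categories, and the fix leaves them there.

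**Conclusion.** The point holds as a small improvement, not as an error. As written, SAP 4.6 would use HbA1c and age in a form that forgoes about 36% to 38% of whatever variance they explain. For an assumed joint R² of 2% to 10%, that equals about 1 to 6 of 152 participants, or 2 to 10 of 250. This rests on normal covariates with linear effects. HbA1c is capped at 10.0% by eligibility, so its share is approximate. The figures apply to the continuous pain-change endpoints; the arithmetic does not cover the responder endpoint.

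A reader might infer that power falls below 80%. It does not: the planned power is unadjusted, and the splits only reduce a gain on top of it.

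The case for the stratum is consistency with the randomisation and protection should baseline pain be screened out, rather than precision. Whether covariates should be selected by significance test at all is a separate and larger question.

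**What to change.** State in SAP 4.6 that HbA1c and age enter the efficacy models as continuous covariates, and that their two-level groupings serve only the subgroup tables and the MOTH matching cells. State also that the randomisation stratum (baseline ADPS <7 / ≥7) is carried in the primary and secondary efficacy models alongside continuous baseline pain, if SAP 8.4.1 does not already say so. In SAP 7.6.1, state that HbA1c and age are continuous in Step 2 of the multiple imputation; leave MOTH as it is.

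The cost is a few sentences and a changed model statement. Continuous terms use no more degrees of freedom than two-level ones, and the stratum adds at most one. No new data are needed.
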